4.1.1 Summaries by Age Categories

In general, summaries by age for PTPs will include age <12 years and ≥ 12 years. In some cases, e.g. for 4 months safety update, additional age categories (age <6 years, ≥ 6 years to <12 years, ≥ 12 years to <18 years, <18 years and ≥ 18 years) will be needed.

Summaries by age for PUPs will include age <6 years and ≥ 6 years to ≤ 12 years.

4.1.2 Reference Date and Study Day

Timing of all safety events, interventions, and findings will be relative to the reference date. The reference date for this study will be the date of the first dose of study medication in this study.

Study day for events on or after the date of the first dose will be defined as the number of days from the date of the first dose of study medication in this study, plus 1 day. Therefore, the date of the first dose will be defined as Day 1. For events before the date of the first dose, study day will be derived as the difference in days between the date of the first dose and the date of interest. Thus, the day before the date of the first dose will be defined as Day -1.

4.1.3 Baseline and Changes from Baseline

Unless otherwise indicated, baseline is defined as the Day-1 visit in this study, and baseline assessments are the last assessments prior to the first dose of study medication in this study. Assessments that are obtained after the first dose of study medication in this study will be considered post-baseline values. If measurement of a variable is not made on a given subject prior to the first dose of study medication, then that subject will be considered not to have a baseline value for that variable. Change from baseline is defined as post-baseline assessment minus baseline assessment.

4.1.4 Handling Partial Dates

A date is a valid partial date if the day is missing, or the day and the month are missing. Where appropriate, the algorithm outlined in Table 1 will be applied to accommodate partial dates.

Table 1. Handling of Partial Dates

Date	Missing Element(s)	Imputation
Start date	Day and Month	First day of the year
	Day	First day of the month
Stop date	Day and Month	Last day of the year
	Day	Last day of the month

4.1.5 Early Withdrawal or Missing data

Apart from the handling of partial dates, and derivation of annualized bleeding rates, no imputation due to withdrawals or missing data will be applied for analyses of efficacy or safety endpoints.

4.1.6 Adjustment for Covariates

There will be no adjustments for covariates.

4.1.7 Considerations for Multi-Center Studies

There will be no pooling of centers for the purpose of analyses.

4.2 Study Periods

This section outlines the separate study periods that are defined for the purposes of the statistical analyses. The study periods are based on the reason for dosing of CSL654 in this study. The PK, prophylaxis treatment, surgery substudy and subcutaneous substudy periods will be treated as disjoint periods for the analyses of efficacy.

The partitioning of the PK, prophylaxis treatment, and substudy periods is described in Table 2.

Table 2. Study periods

Period	Definition
PK	Start: administration of the first rIX-FP infusion in the PK evaluation period. Stop: at the time of the last PK sample; or when the subject received a FIX product for prophylaxis; whichever occurred first.
x^a day prophylaxis regimen	Start: administration of the first x -day infusion. Stop: x days after the last rIX-FP infusion, or with the administration of a different regimen, or start of another period, or at the End of Study visit; whichever occurred first.
Surgery Substudy	Surgery (Major or Minor) Start: administration of first rIX-FP infusion in preparation for the surgery. Stop: 28 days after the surgical procedure or at the End of Substudy visit for the surgery substudy, whichever occurred last.

^a x denotes 7, 10, 14, or 21 (-day prophylaxis regimen).

4.3 Interim Analyses

No formal interim analyses are planned for the purpose of futility or safety stopping.

The following analyses are planned before study closure:

1. The final analysis of the SC substudy data will be conducted when all subjects have completed the SC substudy.
2. The final analysis of PTPs (including surgical data from PTPs) will be conducted when all PTPs have completed the study.

In addition, safety, efficacy and/or PK data and subject characteristics may be reported to regulatory authorities before study closure.

4.4 Disposition of Subjects

Subject disposition (subject populations) will be presented for all subjects who participated in the study by study arm, age (as described in [Section 4.1.1](#)) and total. Summaries of disposition will include the number of enrolled subjects and counts and percentages of subjects in the safety, efficacy, PP, PK, surgical, and SC safety populations, if applicable. Additionally, the summary of disposition will include counts and percentages of subjects' initial and final assigned prophylaxis regimens overall and by regimen (3-day, 7-day, 10-day, 14-day, and 21-day, if applicable).

The number and percentage of subjects who completed the study and did not complete the study, and the reasons for discontinuation from the study (adverse event(s), death, lack of efficacy, lost to follow-up, other, physician decision, protocol violation, study terminated by sponsor, and withdrawal by subject) will be summarized. Reasons for study discontinuation for PUPs due to adverse event, protocol violation, and other (specified) will be further categorized as those associated with Coronavirus Disease 2019 (COVID-19) and those not associated with COVID-19. Other reason specified will be based on free text containing the terms "COVID" or "Coronavirus".

The total number of screened subjects and screen failures also will be displayed. Subject disposition will be summarized separately for all PTPs and all PUPs.

A separate summary of subjects who failed screening including the total number of subjects screened for the study, the count and percentage of subjects who failed screening, and the reasons for failing screening (screen failure, adverse event, lost to follow-up, physician decision, protocol violation, and withdrawal by subject) will be provided.

Summaries of subject populations by geographic region and country of enrollment will be provided by arm, age group, and total. Country will be displayed within region (North American, Europe, Middle East, Asian Pacific, Oceania, and Africa, if applicable). For each country, the number and percentage of subjects enrolled, and the number and percentage of subjects in each of the safety, efficacy, PP, PK, surgical, SC safety, and SC PK populations will be displayed, if applicable.

Deviations from the inclusion/exclusion criteria will be summarized for all enrolled subjects. The summary will include counts and percentages of subjects with any deviation from inclusion criteria and counts and percentages of subjects with deviations from each inclusion criteria as applicable. A similar display will be provided for the exclusion criteria.

4.5 Protocol Deviations

The number and percentage of subjects who had major protocol deviations will be summarized for the safety populations.

Major protocol deviations will be summarized by categories of deviation. All protocol deviations that have been documented throughout the study will be presented in subject listings for all subjects. Separate listings will be provided for PTP subjects in the efficacy population who were excluded from the PP population.

The summary of major protocol deviations for PUPs will also include deviations associated with COVID-19, and the source listing will flag these deviations.

Planned visits that were missed due to COVID-19 will be summarized for PUPs. A by-subject listing of missed visits due to COVID-19 will be included.

4.6 Demographics and Baseline Characteristics

Demographics will be summarized using frequency counts and percentages for the following: race (American Indian/Alaska Native, Asian, Black or African American, Native Hawaiian/Other Pacific Islander, White, and Other), ethnicity (Hispanic or Latino, not Hispanic or Latino, not reported, and unknown), body mass index (BMI) category ($<30 \text{ kg/m}^2$ and $\geq 30 \text{ kg/m}^2$), and Geographic Region. Age, height, weight, and (BMI) at screening for this study will be summarized with descriptive statistics for continuous variables.

Age will be determined for all subjects using date of birth and the date of informed consent (i.e. date of screening) for Study CSL654_3003. The value of age will be derived as the integer part of $(\text{date of screening} - \text{date of birth})/365.25$. Partial dates will be handled as outlined in [Table 1](#). BMI will be derived as $\text{weight (kg)} / (\text{height (m)})^2$. BMI will be summarized as a continuous variable and categorized as $<30 \text{ kg/m}^2$, $\geq 30 \text{ kg/m}^2$.

Demographics will be summarized for the Safety population overall, and presented by arm, age group (as described in [Section 4.1.1](#)), and total.

The following baseline characteristics will be summarized and/or listed for PTPs and PUPs:

- Medical/surgical history will be coded using the Medical Dictionary for Regulatory Activities (MedDRA) Version 21.0 for PTPs and Version 23.1 or higher for PUPs. These will be presented by system organ class (SOC) and preferred term (PT). Past as well as active (i.e., still on-going at Screening) medical histories will be displayed.
- Hemophilia B history as follows:
 - time (months), defined as $(\text{date of informed consent} - \text{date of diagnosis})/30.4375$, since first diagnosis of severe hemophilia B (factor IX activity $\leq 2\%$) (for Arm 3) or time (months) since first diagnosis of moderate to severe hemophilia B (for Arm 4)
 - time (weeks) since last factor IX level $< 2\%$ - Arm 3 only
 - estimated or documented treatment days (EDs) at the screening visit – Arm 3 only
 - number and type of bleeding events in the past 12 months – Arm 3 only
 - family history of inhibitors against FIX – Arm 4 only
 - genotype
 - presence of chronic hemarthrosis, hemophilic arthropathy, and target joints

The following baseline characteristics will be summarized and listed only for subjects in Arm 3:

- FIX treatment history including
 - time since receiving the first prophylaxis treatment (months)
 - most recent treatment modality (prophylaxis, on-demand) prior to study entry
 - modalities (routine prophylaxis, on-demand, post-surgery, and prevention prior to activity) in the previous 6 months
 - product type (pdFIX, rFIX, or rIX-FP) in the previous 6 months
 - IU/kg per prophylaxis dose and times per week for prophylaxis in the previous 6 months
 - weekly prophylaxis dose (IU/kg) (calculated as IU/kg per prophylaxis dose multiplied by times per week) in the previous 6 months
 - IU/kg for on-demand in the previous 6 months; and
 - total dose [IU] administered in the previous 6 months

4.7 Exposure Days and Time on Study

The number of EDs will be calculated in the clinical database for each subject and reported for both this study and over the cumulative experience of rIX-FP exposure in lead-in studies (CSL654_3001 and CSL654_3002). Exposure to rIX-FP will be summarized separately for the substudies (surgery and SC). An ED of rIX-FP is defined as any day that the subject receives an infusion of rIX-FP regardless of the number of infusions on that day or reason for the infusion(s). The number of EDs for subjects in lead-in studies will be imported into the CSL654_3003 database and used to summarize the total number of EDs across studies.

Summaries of exposure and time on study will include descriptive statistics for time on study in days, weeks, and months, total EDs in Study CSL654_3003, total EDs across all CSL654 studies, and the total dose (IU, IU/kg, IU/kg/year, and IU/kg/month) of CSL654 received only in Study CSL654_3003, and will be displayed by arm, prophylaxis regimen, age groups ([Section 4.1.1](#)), and total.

The number of EDs will be summarized as both a continuous and categorical variable. The following categories will be presented as applicable for PTPs:

- < 50 EDs
- ≥ 50 EDs
- ≥ 75 EDs
- ≥ 100 EDs
- ≥ 150 EDs
- ≥ 200 EDs

- ≥ 250 EDs
- ≥ 300 EDs

The following categories will be presented as applicable for PUPs:

- < 50 EDs
- ≥ 50 EDs
- ≥ 75 EDs
- ≥ 100 EDs

For PTPs, cumulative distribution function (CDF) plots will be provided for EDs in CSL654_3003 and total EDs across all CSL654 lead-in studies. The CDF plots will be generated using the PTP safety population.

For PUPs, CDF plots will be provided for EDs in CSL654_3003 PUPs. The CDF plots will be generated using the PUP safety population.

Time on study

Time on study (days) will be derived as:

$$(\text{end of study visit date}) - (\text{study medication start date}) + 1.$$

Time on study in months will be calculated as:

$$\text{Time on study (days)} / 30.4375$$

Exposure and time on each regimen will be the sum of accumulated time (in days) on each regimen in Study CSL654_3003. For example, a subject who was on the 7-day regimen for 20 days, followed by 30 days on the 14-day regimen, and then went back on the 7-Day regimen for 20 days will have a total of 40 days on the 7-day regimen.

Descriptive statistics will be provided for exposure and time on study by prophylaxis regimen and age for the PTP safety population overall and for the following subgroups:

- subjects ≥ 18 years in the PTP safety population who switched from 14-day regimen to 21-day regimen
- subjects in the PTP safety population who switched to the 21-day regimen (subjects ≥ 18 years are allowed to switch to 21-day regimen) compared with subjects ≥ 12 years in the PTP safety population who did not switch to the 21-day regimen
- subjects < 12 years in PTP safety population on 14-day regimen
 - paired comparisons for subjects who participated in both the 7-day regimen and 14-day regimen in 3003 (total 14-day regimen in 3003 presented on the same display)
 - paired comparisons for subjects who participated in the 7-day regimen in 3002 and/or 3003 and the 14-day regimen in 3003

- subjects <12 years in the PTP safety population who switched to the 14-day regimen compared with subjects <12 years in the PTP safety population who did not switch to the 14-day regimen

Descriptive statistics will be provided for time on study, exposure days, and total dose (IU and IU/kg) by age group (<6 vs 6 to ≤12 years) for the PUP safety population.

Subject listings of exposure for PTPs will include the number of EDs, duration on study (days, weeks, and months), and total dose (IU, IU/kg, IU/kg/year, and IU/kg/month) in Study CSL654_3003. Listings of rIX-FP administration for PTPs will include location of administration (home, hospital, or study site), infusion start date and time, lot, lot number, and vial, total IU administered, by whom treatment was administered (subject, caregiver, or site staff), calculated dose administered (IU/kg), reason for administration, and new bleeding event.

Subject listings of exposure for PUPs will include total dose (IU), number of EDs, and duration on study (days, weeks, and months). Listing of rIX-FP administration for PUPs will include location of administration (home, hospital, or study site), infusion start date and time, log, lot number, vial number, total dose (IU) administered, treatment operator (subject, caregiver, or site staff), calculated dose administered (IU/kg), and reason for administration. If it's for a bleeding event, whether it's for a new bleeding event or an existing bleeding event will be indicated.

Listings of rIX-FP administration will be provided separately for the surgery and SC substudies for the PTP safety population

4.8 Dose Assignment and Adjustment

For PTPs, dose assignment by age (as described in [Section 4.1.1](#)) and overall will be presented by prophylaxis regimen and will include summary statistics for the initial (first) assigned dose (IU/kg), most recent assigned dose (IU/kg), and all assigned doses (IU/kg).

Prophylaxis regimen shifts for PTPs will be presented by regimen and age. Displays will include the initial and final regimen for each study arm. PTPs who participated in multiple regimens will be counted only once in each regimen in which they participated. Prophylaxis regimen shifts will not be summarized for PUPs.

For PUPs, dose assignment by age and overall will be presented for the following items:

- Initial and most recent assigned prophylaxis dose (IU/kg)
- All assigned prophylaxis doses (IU/kg)
- Initial and most recent assigned on-demand dose (IU/kg)
- All assigned on-demand doses (IU/kg)
- Initial and most recent dose received (IU/kg)
- All doses received (IU/kg)

Subject listings for dose assignment and adjustment will include assigned dose, prophylaxis regimen, on-demand dose assignments for joint/muscle and/or deep muscle as applicable, dose and frequency adjustments, modality, and reason for dose adjustment.

4.9 Prior and Concomitant Medications and Nonpharmacological Interventions

Prior medications are medications that started and stopped before the first dose of study medication. Concomitant medications are all medications taken during the study, including medications started before and ongoing at first dose of study medication. All medications will be considered concomitant for subjects in Arms 1 and 2 of the study.

The analysis datasets associated with concomitant medications will contain the flags defined below:

Prior: the start date is either strictly prior to the reference date or missing.

Concomitant: either the start date or the end date is on or after the reference date, or the end date is missing.

Partial dates will be handled as outlined in [Table 1](#). Prior and concomitant medications will be coded using the World Health Organization (WHO) Drug dictionary (March 2018, Enhanced B for PTPs and September 2020, Enhanced B or higher for PUPs). Summaries of prior and concomitant medications will include the preferred drug name within the Anatomical-Therapeutic-Chemical (ATC) level 4 classification and will be presented by arm, age group ([Section 4.1.1](#)), and total. If a subject has multiple occurrences of a medication, then the subject will be presented only once in the respective subject count.

A separate summary of concomitant medications will be provided for PUPs who administer medications for treatment of an adverse event associated with COVID-19. These medications will be flagged in the source listing for concomitant medications.

Subject listings will be provided for nonpharmacological interventions (e.g., physical therapy or a minor surgical procedure performed outside of the surgery substudy) as collected on the eCRF.

4.10 Compliance

Compliance will be defined in terms of the following:

- the prophylaxis schedule, i.e., “prophylaxis compliance”
- the prescribed dose, i.e., “dose compliance”
- time to on-demand treatment of a bleeding event, i.e., “treatment compliance”

Prophylaxis compliance will be derived as:

$$\frac{\text{(number of on-schedule prophylaxis infusions received)}}{\text{(expected number of prophylaxis infusions)}} * 100$$

where on-schedule prophylaxis infusions are injections during the study period that occur at the expected dosing frequency within the defined target days.

Dosing for each prophylaxis regimen is expected to occur within the following target days:

- For the 7-day regimen, injection of rIX-FP occurs between days 6 and 8 after the previous prophylaxis injection.
- For the 10-day regimen (i.e., every 10 days or 3 times per month), injection of rIX-FP occurs between days 8 and 11 after the previous prophylaxis injection.
- For the 14-day regimen, injection of rIX-FP occurs between days 13 and 15 after the previous prophylaxis injection.
- For the 21-day regimen, injection of rIX-FP occurs between days 20 and 22 after the previous prophylaxis injection.

Dose compliance will be derived as follows:

$$(\text{number of doses within 10\% of the prescribed dose}) / (\text{number of doses received}) * 100$$

Treatment compliance will be derived as follows:

$$\frac{(\text{number of bleeding events treated with rIX-FP } < 4 \text{ hours after the start of a bleeding event})}{(\text{number of bleeding events treated with rIX-FP})} * 100$$

A subject will be defined as compliant with each of prophylaxis regimen, dose, or treatment if the compliance is $\geq 80\%$.

Prophylaxis, dose, and treatment compliance will be summarized by prophylaxis regimen in the safety population using descriptive statistics. Summaries will include the number and percentage of subjects who were compliant with their prophylaxis regimen, dose, treatment, the number and percentage of subjects who were $\geq 80\%$ for each measure, and the number and percentage of subjects who were $< 80\%$ compliant for each measure. Subject listings that include all derived compliance measures for each subject will be provided.

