3.2.2 On-demand Treatment of Bleeding Episodes

On-demand treatment with rIX-FP will be used for all bleeding episodes requiring treatment. If a subject experiences a bleeding episode, rIX-FP should be administered within 4 hours after the start of the bleeding episode. The dose of rIX-FP will be determined by the investigator, based on the effective on-demand treatment dose used in the lead-in study and / or the subject's PK data with a minimum rIX-FP dose of 35 IU/kg and a maximum dose of 75 IU/kg. After hemostasis is achieved, maintenance dose(s) of rIX-FP may be prescribed at the discretion of the investigator.

Subjects receiving on-demand treatment for a bleeding episode should maintain or delay (but not skip) the prophylaxis treatment schedule, at the investigator's discretion. The window between the last treatment for the bleeding episode and the next prophylaxis injection should not be longer than the number of days of the current treatment interval (ie, 7, 10, 14, or 21 days). In addition, any two injections of rIX-FP should be at least 24 hours apart.

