6.3 TREATMENT COMPLIANCE

Subjects will record the dose, time of the dose and rIX-FP consumption for prophylaxis, prevention and on-demand treatment of bleeding episodes in the eDiary. In addition, subjects will bring all of their used vials (and unused, if requested) of rIX-FP to the study site at every visit. Treatment compliance will be monitored by counting the number of returned vials, the results of which will be recorded in the Drug Accountability Log. rIX-FP use, as reported by the subject in the eDiary, will also be reconciled to the returned vials.

For prophylaxis treatment, a subject will be regarded as compliant with treatment if both criteria below are met:

- **Regimen compliance:** The subject receives at least 80% of the injections of rIX-FP at the scheduled injection frequency during the study period where dosing is expected to occur within the following target days:
 - For the 7-day treatment interval: injection of rIX-FP occurs between Days 6 and 8 after the previous prophylaxis injection.
 - For the 10-day treatment interval (ie, every 10 days or 3 times per month): injection of rIX-FP occurs between Days 8 and 11 after the previous prophylaxis injection.
 - For the 14-day treatment interval: injection of rIX-FP occurs between Days 13 and 15 after the previous prophylaxis injection.
 - For the 21-day treatment interval (not applicable to subjects in France): injection of rIX-FP occurs between Days 20 and 22 after the previous prophylaxis injection.
- **Dose compliance:** The subject receives 80% to 120% of the prescribed dose, based on the actual dose, for at least 80% of injections.

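### The compliance scoring in protocol 6.3 and SAP 4.10 does not separate delays permitted after a bleed from non-adherence, and SAP 4.10 applies a dose tolerance different from protocol 6.3 without listing the change

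*SAP*

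**What the plan says.** **Schedule.** Protocol 3.2.2 covers what happens to prophylaxis after a treated bleed: "Subjects receiving on-demand treatment for a bleeding episode should maintain or delay (but not skip) the prophylaxis treatment schedule", at the investigator's discretion. It sets a limit: "The window between the last treatment for the bleeding episode and the next prophylaxis injection should not be longer than the number of days" in the current interval. It also asks for at least 24 hours between any two injections.

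SAP 4.10 defines prophylaxis compliance as on-schedule infusions divided by the expected number of infusions. On-schedule is counted from the previous prophylaxis injection:

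- 7-day: "For the 7-day regimen, injection of rIX-FP occurs between days 6 and 8 after the previous prophylaxis injection"
- 10-day: "injection of rIX-FP occurs between days 8 and 11 after the previous prophylaxis injection"
- 14-day: "For the 14-day regimen, injection of rIX-FP occurs between days 13 and 15 after the previous prophylaxis injection"
- 21-day: "For the 21-day regimen, injection of rIX-FP occurs between days 20 and 22 after the previous prophylaxis injection"

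Protocol 6.3 has the same four windows. Neither section makes an exception for a delay after a bleed, and SAP 4.10 does not define the expected number of infusions.

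**Dose.** Protocol 6.3, for prophylaxis: "The subject receives 80% to 120% of the prescribed dose, based on the actual dose, for at least 80% of injections". SAP 4.10 instead takes doses within 10% of the prescribed dose over all doses received, and calls a subject compliant at 80% or more. Protocol 6.2 separately requires the final dose, after rounding to full vials, to be within 10% of the prescribed dose. SAP section 8 lists several departures from the protocol but not this one. The SAP introduction says its methods supersede the protocol's.

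**The concern.** A compliance rate is read as evidence that a regimen was taken as assigned. Here a subject can follow protocol 3.2.2 exactly and still be scored off-schedule. What lowers the score is then partly bleeding. Because a longer interval has fewer infusions per year, each off-schedule dose costs more there, so a reader comparing regimens could take a lower figure at 14 or 21 days as poorer adherence.

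The dose rate has a separate problem. A reader who knows the protocol's compliance definition will assume 80–120%, while the table will show the share within 10%.

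The schedule conflict also reaches beyond tables. Protocol 3.2.1.2 lets compliance inform a change of interval, and protocol 4.2.1 lists failure to follow the assigned schedule among the grounds on which a subject may be discontinued. Sections 3.2.2 and 6.3 must therefore be reconciled so that it is clear what following the schedule means.

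**Working it through.** The documents state no adherence figure, so there is none to reproduce.

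**Example.** A weekly subject doses on Day 0, treats a bleed on Day 5 and takes the next prophylaxis dose on Day 12. The gap from the bleed treatment is 12 − 5 = 7 days, which meets 3.2.2. The gap from the previous prophylaxis dose is 12 days, outside 6–8, so it is off-schedule.

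**Room for off-schedule doses.** For interval x, infusions per year = 365.25/x. The score falls below 80% when off-schedule doses exceed 0.2 × 365.25/x.

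| Interval (days) | 7 | 10 | 14 | 21 |
|---|---|---|---|---|
| Infusions per year | 52.2 | 36.5 | 26.1 | 17.4 |
| Off-schedule doses per year to fall below 80% | >10.4 | >7.3 | >5.2 | >3.5 |

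**Effect of permitted delays.** Inputs and assumptions:

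- Bleed rate: 4.4 per year, the mean total rate on weekly prophylaxis in the phase 1/2 study (protocol 1.2.3.2; n = 13, SD 4.7), assumed equal at every interval. Rates of 1, 2 and 6 are also shown.
- Bleeds follow a Poisson process and are treated at once. There are no other late or missed doses.
- After a bleed, the next dose is either kept on schedule or delayed to the 3.2.2 limit (bleed treatment + x days). The share delayed is unknown, so 0, one half and all are shown.

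Simulation of 4,000 subjects per cell over one year gives mean schedule compliance (%):

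| Bleeds/year, share delayed, denominator | 7 | 10 | 14 | 21 |
|---|---|---|---|---|
| 4.4, none, either | 100 | 100 | 100 | 100 |
| 4.4, half, infusions received | 96.4 | 94.8 | 92.3 | 88.7 |
| 4.4, all, infusions received | 93.1 | 89.7 | 85.4 | 78.5 |
| 4.4, all, calendar days/x | 88.7 | 84.6 | 77.5 | 69.1 |
| 1, all, infusions received | 98.4 | 97.5 | 96.4 | 94.6 |
| 2, all, infusions received | 96.7 | 95.3 | 93.0 | 89.5 |
| 6, all, infusions received | 90.5 | 86.3 | 80.7 | 72.0 |

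Hand check of the third row: a fully delayed dose stays in the window only if no bleed falls after the first day of the interval, so the on-schedule share is about exp(−λ(x − 1)) with λ = 4.4/365.25 = 0.01205 per day. For x = 7, exp(−0.0723) = 93.0%. For x = 21, exp(−0.241) = 78.6%.

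Share of subjects reaching 80% at 4.4 bleeds a year, all doses delayed: 99.9/96.3/77.8/54.6% for 7/10/14/21 days with infusions received, and 94.2/77.0/47.2/23.9% with calendar days. The undefined denominator alone moves the 14-day mean from above 80% (85.4) to below it (77.5).

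If delays within the 3.2.2 limit counted as on-schedule, every cell would be 100%, since the model contains no other off-schedule doses.

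**Dose rule.** For a normal deviation centred on the prescribed dose with an assumed SD s, the share within c% is 2Φ(c/s) − 1.

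| SD (% of prescribed dose) | 5 | 8 | 10 |
|---|---|---|---|
| Within 10% | 95% | 79% | 68% |
| Within 20% | >99.9% | 99% | 95% |

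The SAP tolerance is stricter. The interval does not enter the formula.

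**The case against.** The strongest reply is that the SAP did not invent the schedule rule: it uses the four windows of protocol 6.3, the section that defines compliance. That stands. The conflict is between protocol 3.2.2 and 6.3, and the SAP carries it over, so editing SAP 4.10 alone would create a new mismatch.

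Second, the 10% figure has a source in protocol 6.2. That also stands, and it means a dose 10–20% off meets 6.3 but misses 6.2. It does not explain why the compliance definition changed without an entry in section 8.

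Third, the size depends on assumptions. Protocol 3.2.2 allows the schedule to be maintained as well as delayed. The 4.4 rate comes from 13 weekly subjects, of whom 8 reported treated bleeds, and SAP section 8 expects half of subjects to have none. All of this is fair, which is why a range is given.

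Fourth, SAP 3.1 says Arms 1 to 3 are already analysed and SAP 3.4 says this version focuses on Arm 4, whose prophylaxis is weekly. The interval effect therefore concerns tables already reported. Nor is compliance the only evidence of delivery: SAP 4.7 and 4.11 also summarise exposure, time on regimen and injections per month and year.

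A reader might infer that reported adherence is wrong, or that the whole compliance analysis is biased against longer intervals. The documents do not support either. They give no delay frequency, the dose criterion is the same at every interval, and no visible analysis relates compliance to bleeding.

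**Conclusion.** The point holds as a defect of definition and disclosure. Under the stated rules, doses that follow protocol 3.2.2 can be labelled off-schedule, and dose compliance is reported under a definition different from protocol 6.3.

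The schedule effect ranges from nothing, if no dose is delayed, to the all-delayed figures above. It grows with the interval only if bleed rates are equal across intervals and doses are in fact delayed. For weekly Arm 4 subjects it is modest: even with every dose delayed at 4.4 bleeds a year, the mean is 93.1% (infusions received) or 88.7% (calendar days).

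Compliance is a descriptive summary. No hypothesis test uses it, the per-protocol definition does not name it, and SAP 3.6.5 plans no per-protocol analysis for previously untreated patients.

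**What to change.** - **Protocol:** reconcile 3.2.2 with 6.3, and 6.2 with 6.3, for compliance scoring. Which figures should govern is for the sponsor to decide.
- **SAP 4.10, schedule:** count the first prophylaxis injection after a treated bleed as on-schedule if it falls within the 3.2.2 limit, or drop it from numerator and denominator. Define the expected number of prophylaxis infusions, stating whether it means infusions received or calendar days divided by the interval.
- **SAP 4.10, dose:** report the protocol 6.3 criterion, on prophylaxis injections, beside the within-10% criterion.
- **SAP section 8:** list the dose-compliance change with its reason.
- **Scope:** apply this to the Arm 4 tables. Where compliance of previously treated patients is cited, add a footnote that permitted delays were not separated from non-adherence.

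The cost is wording, one changed derivation and one added row. Infusion dates, times, doses and reasons are already collected, so no new data are needed. Re-analysis of the reported tables is not required.
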